#### **6.4.2 AE**

An AE is any untoward medical occurrence in a patient or clinical investigation subject administered a pharmaceutical product and that does not necessarily have a causal relationship with this treatment. An AE can therefore be any unfavorable and unintended sign (including an abnormal laboratory finding), symptom, or disease temporally associated with the use of a medicinal (investigational) product, whether or not related to the medicinal (investigational) product.

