#### **6.3. Study procedures**

##### **6.3.1 Study procedures**

##### **6.3.2 Intervention**

##### **(incubator)**

This product was developed by ATOM and IGPC as shown in Appendix. The incubator is made of vinyl and water tank made of plastic. The mattress uses thermal insulation to prevent direct contact with the newborn. In experiments, we have confirmed that incubators can be kept warm for more than 3 hours with a single hot water change. Also in the experiment, the temperature of the doll's surface did not become so high as to cause burns.

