#### **6.4.3 SAEs**

Serious adverse event or serious suspected adverse reaction: An adverse event or suspected adverse reaction is considered “serious” if, in the view of either the investigator or sponsor, it results in any of the following outcomes: Death, a life-threatening adverse event, inpatient hospitalization or prolongation of existing hospitalization, a persistent or significant incapacity or substantial disruption of the ability to conduct normal life functions, or a congenital anomaly/birth defect. Important medical events that may not result in death, be life-threatening, or require hospitalizations may be considered serious when, based upon appropriate medical judgment they may jeopardize the patient or subject and may require medical or surgical intervention to prevent one of the outcomes listed in this definition.

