#### **6.4.4 Relationship to Study Product**

The assessment of the AE’s relationship to study product will be done by the licensed study physician indicated on the Form FDA 1572 and the assessment will be part of the documentation process. Whether the AE is related or not, is not a factor in determining what is or is not reported in this trial. If there is any doubt as to whether a clinical observation is an AE, the event should be reported.

In a clinical trial, the study product must always be suspect. The relationship to study product will be assessed for AEs using the terms related or not related:

Relate-There is a reasonable possibility that the study product caused the AE.

Reasonable possibility means that there is evidence to suggest a causal relationship between the study product and the AE.

Not Related – There is not a reasonable possibility that the administration of the study product caused the event

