#### **6.4.5 Adverse Event Evaluation**

The investigator or designee is responsible for ensuring that all adverse events (both serious and non-serious) observed by the clinical team or reported by the subject which occur after the subject has signed the informed consent are fully recorded in

the subject's medical records. Source documentation must be available to support all adverse events.

A laboratory test abnormality considered clinically relevant (e.g., causing the subject to withdraw from the study, requiring treatment or causing apparent clinical manifestations, result in a delay or dose modification of study treatment, or judged relevant by the investigator), should be reported as an adverse event.

The investigator or sub-investigator (treating physician if applicable) will provide the following for all adverse events (both serious and non-serious):

- Event term (as per CTCAE)
- Description of the event
- Date of onset and resolution
- Outcome of event

**An expected adverse event** is an event previously known or anticipated to result from participation in the research study or any underlying disease, disorder, or condition of the subject. The event is usually listed in the Investigator Brochure, consent form or research protocol.

**An unexpected adverse event** is an adverse event not previously known or anticipated to result from the research study or any underlying disease, disorder, or condition of the subject.

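### The adverse-event definition is written for a drug, but the study product is an incubator, so harms may be captured inconsistently and malfunctions without injury have no route into the safety record

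*Protocol*

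**What the plan says.** Protocol section 6.4.2 gives the definition in two sentences. The first ties an adverse event to "any untoward medical occurrence in a patient or clinical investigation subject administered a pharmaceutical product". The second extends it to any unfavourable sign, symptom or disease "temporally associated with the use of a medicinal (investigational) product, whether or not related to the medicinal (investigational) product".

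The intervention is described in section 6.3.2: "The incubator is made of vinyl and water tank made of plastic". The component table in the Appendix lists a hood, a mattress and hot-water bottles. No investigational medicine is given.

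The rest of section 6.4 builds on the definition:

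- 6.4.3 starts the definition of a serious event from the same term: "An adverse event or suspected adverse reaction is considered" serious if it has one of the listed outcomes.
- 6.4.4 speaks of the study product. It states "In a clinical trial, the study product must always be suspect" and "If there is any doubt as to whether a clinical observation is an AE, the event should be reported".
- 6.4.5 requires that all adverse events "which occur after the subject has signed the informed consent are fully recorded". Among its examples of a relevant laboratory abnormality is one that would "result in a delay or dose modification of study treatment".
- 6.4.6 says that all adverse events are reported, and 6.4.7 requires serious ones to reach the lead investigator within 24 hours.

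**The concern.** The definition decides what enters the safety record, and its exposure term names something this trial does not give. An infant exposed only to the incubator does not meet the first sentence as written. Whether the second sentence covers the infant depends on whether an incubator can be read as a medicinal (investigational) product.

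There is a second gap that better reading of the exposure term would not close. The definition covers medical occurrences, signs, symptoms and diseases in the infant. A device that leaks, is assembled wrongly or has a failed hood, but has not yet hurt anyone, is none of these.

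This matters because the protocol expects only at least 6 infants, and section 9.3 already describes the risk as almost nil. An empty adverse-event list could be read as supporting that statement when part of what can go wrong had no place to be written down.

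**Working it through.** No figure in the protocol can be reproduced here: it states no adverse-event rate, threshold or event-based stopping rule. The check is to set the rules side by side and follow three kinds of event through them.

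**1. Harm to an infant in the incubator who has received no drug (for example a scald of the back, the hazard named in the Appendix).**
- 6.4.2, first sentence: not met, since no pharmaceutical product was administered.
- 6.4.2, second sentence: unclear. The bracketed word investigational could take in the incubator; the word medicinal points away from it.
- 6.4.4: the event is a clinical observation whose status is in doubt, so it should be reported and assessed against the study product, which can only be the incubator.
- Result: captured, provided staff recognise the doubt and use 6.4.4.

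**2. The same harm in an infant who has received any routine drug.**
- 6.4.2, first sentence: met. The sentence does not require the drug to be investigational and disclaims causality.
- Result: captured directly. The protocol does not say how many infants receive a drug. With 6 infants the number could be anywhere from 0 to 6.

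Two infants with the same injury thus enter by different routes, one explicit and one by inference. This is the risk of inconsistent capture.

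**3. A malfunction without injury (leaking bottle, hood failure, use error).**
- 6.4.2: not met under either sentence, and still not met if incubator is substituted for pharmaceutical product, because nothing medical has happened to the infant.
- 6.4.4: the doubt rule concerns a clinical observation. A leak or an assembly error is hardly one.
- Section 6.1.1 data sheet: the columns cover vital signs, temperatures, humidity, oxygen and milk intake. None is for a leak, a hood failure or a use error.
- Result: no route into the record.

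**Heat loss and overheating** are a partial exception, because section 6.1.1 records inside, outside and water temperature. The coverage of those rows can be counted:
- Rows after the start: 15, 30, 45 and 60 minutes (4 rows), then 90 to 360 minutes in steps of 30: (360 − 90)/30 + 1 = 10 rows. Total 4 + 10 = 14.
- Observation under section 6.1.2, step 11: 24 hours = 24 × 60 = 1,440 minutes. The rows span 360/1,440 = 25% of it, leaving 18 hours without a printed row.
- If the 30-minute interval of step 7 is assumed to continue to 24 hours, the sheet would need 4 + (1,440 − 60)/30 = 4 + 46 = 50 rows, against the 14 printed.

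**Downstream rules.** Sections 6.4.3 and 6.4.5 to 6.4.7 use the 6.4.2 term and do not restate it, so the mismatch carries into serious events, recording and the 24-hour report. The window is also open-ended: 6.4.5 starts it at consent, while 6.4.6 refers to a period that it does not define.

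**The case against.** The strongest reply is that section 6.4 should be read as a whole. Section 6.4.4 makes the study product always suspect, says that relatedness does not decide what is reported, and sends doubtful observations to reporting. The doubt rule does not presuppose that the event already meets 6.4.2. The incubator is the only product under study, so a sensible investigator would report a scald or hypothermia. This stands, and it limits the first gap to a risk of inconsistency.

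A reader might infer something stronger: that the rule returns zero incubator events whatever happens, so that a safe and an unsafe device would give the same result. The documents do not support this. It needs 6.4.2 applied alone, against 6.4.4, and it fails for any infant given a routine drug. A reader might also infer that malfunctions without injury are the likeliest safety signal in this trial; nothing in the protocol establishes that.

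It can further be said that heat loss and overheating are already collected as main study parameters, and that section 6.1.2 provides for a chamber that becomes too warm. This holds for the printed time points. It does not help with leaks, hood failure or use error, nor after the last row.

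Finally, a device-deficiency category may look like an added preference. But section 1 itself names insufficient heat retention as a risk, and section 3.3 aims to verify that local staff can learn to operate the device quickly. Device failures and use errors are therefore within what the study sets out to learn. Nor is the definition something commonly left to a statistical analysis plan: the protocol has fixed it, and fixed it for a different kind of product.

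**Conclusion.** The point holds as a mis-specified definition. The adverse-event term in 6.4.2 does not fit the study product, and the later safety rules inherit it. Two consequences follow. Harms to infants are likely to be reported, but for infants given no drug this rests on the doubt and study-product rules of 6.4.4, so capture may vary between staff. Malfunctions without injury are left out, even on a generous reading of the exposure term.

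The size cannot be expressed as a number of missed events, because the protocol gives no event rates and does not say how many infants receive a drug. The one countable element is that the sheet's rows cover 6 of 24 observed hours. This assumes that the sheet in 6.1.1 is the working form and that no extra rows or device log exist elsewhere.

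The dose-modification phrase in 6.4.5 is a symptom of the same drug-trial wording. It is one item in a list of alternatives that ends with the investigator's judgement, so it excludes nothing.

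**What to change.** - **6.4.2:** define an adverse event as any untoward medical occurrence in an enrolled infant from consent to discharge, whether or not related to the incubator. This removes the drug-exposure term and also settles the undefined period in 6.4.6.
- **6.4.4:** state that the study product is the incubator, meaning hood, mattress and hot-water bottles.
- **Case report form:** add one line for device deficiencies (malfunction, leak, failure to hold heat, overheating, use error), completed even when the infant is unharmed. Where a deficiency could have led to a serious event, report it under the existing 24-hour rule of 6.4.7.
- **6.1.1 and 6.1.2:** reconcile the sheet's last row with the stated length of observation, so that it is clear which readings are expected.
- **6.4.5:** removing the dose-modification wording is optional tidying and changes no result.

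The cost is a protocol wording change and one form line. The downside is that a few more events will be recorded and reported.

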#### **6.4.3 SAEs**

Serious adverse event or serious suspected adverse reaction: An adverse event or suspected adverse reaction is considered “serious” if, in the view of either the investigator or sponsor, it results in any of the following outcomes: Death, a life-threatening adverse event, inpatient hospitalization or prolongation of existing hospitalization, a persistent or significant incapacity or substantial disruption of the ability to conduct normal life functions, or a congenital anomaly/birth defect. Important medical events that may not result in death, be life-threatening, or require hospitalizations may be considered serious when, based upon appropriate medical judgment they may jeopardize the patient or subject and may require medical or surgical intervention to prevent one of the outcomes listed in this definition.

#### **6.4.4 Relationship to Study Product**

The assessment of the AE’s relationship to study product will be done by the licensed study physician indicated on the Form FDA 1572 and the assessment will be part of the documentation process. Whether the AE is related or not, is not a factor in determining what is or is not reported in this trial. If there is any doubt as to whether a clinical observation is an AE, the event should be reported.

In a clinical trial, the study product must always be suspect. The relationship to study product will be assessed for AEs using the terms related or not related:

Relate-There is a reasonable possibility that the study product caused the AE.

Reasonable possibility means that there is evidence to suggest a causal relationship between the study product and the AE.

Not Related – There is not a reasonable possibility that the administration of the study product caused the event

#### **6.4.5 Adverse Event Evaluation**

The investigator or designee is responsible for ensuring that all adverse events (both serious and non-serious) observed by the clinical team or reported by the subject which occur after the subject has signed the informed consent are fully recorded in

the subject's medical records. Source documentation must be available to support all adverse events.

A laboratory test abnormality considered clinically relevant (e.g., causing the subject to withdraw from the study, requiring treatment or causing apparent clinical manifestations, result in a delay or dose modification of study treatment, or judged relevant by the investigator), should be reported as an adverse event.

The investigator or sub-investigator (treating physician if applicable) will provide the following for all adverse events (both serious and non-serious):

- Event term (as per CTCAE)
- Description of the event
- Date of onset and resolution
- Outcome of event

**An expected adverse event** is an event previously known or anticipated to result from participation in the research study or any underlying disease, disorder, or condition of the subject. The event is usually listed in the Investigator Brochure, consent form or research protocol.

**An unexpected adverse event** is an adverse event not previously known or anticipated to result from the research study or any underlying disease, disorder, or condition of the subject.

#### **6.4.6 Reporting Procedures for Serious Adverse Events**

For the purposes of safety reporting, all adverse events will be reported. Adverse events, both serious and non-serious, and deaths that occur during this period will be recorded in the source documents. All SAEs should be monitored until they are resolved or are clearly determined to be due to a subject's stable or chronic condition or intercurrent illness(es). Related AEs will be followed until stabilization.

#### **6.4.7 SAE Reporting Requirements**

Participating investigators (all sites) must report all serious adverse events to the Lead Site Principal Investigator within 24 hours of discovery or notification of the event. The participating investigator must also provide follow-up information on the SAE until final resolution.

Investigative sites will report adverse events to their respective IRB according to the local IRB's policies and procedures in reporting adverse events.

## **7. DATA MANAGEMENT AND STATISTICAL ANALYSIS**

### **7.1 Data management**

All patients will be identified with a unique study identification code. A logbook with the matching between patient number and name will be stored digitally and in paper. The paper version will be stored behind a lock and the digital form will be protected with a

password. The logbook will be the only document containing patient identifier information. Data will be stored an additional 15 years after the study's completion.

### **7.1.2 Data capture**

Data is collected on paper checklists and case report forms (CRFs) and subsequently transcribed onto an Internet-based electronic CRF (<https://www.kobotoolbox.org>). Access to the data-entry system is protected by a personalized username and password. Patients are identified with a study identification code, hence there will be no patient identifier data transcribed on the online CRF.

### **7.1.3 Data sharing**

Data derived from this study will be shared with the clinical team directly responsible for patient's care and with hospital leadership and management team for monitoring and/or audit purposes. Specifically, a copy of the final expert report performed with the conventional apparatus will be attached to the patient's clinical chart to be visualized by the clinical team responsible for patient's care. After publication of the primary results, on request the pooled dataset will be available for secondary analysis, after judgment and approval of scientific quality and validity of the proposed analysis by the steering committee.

## **7.2 Statistical analysis**

This study only records biological parameters and temperature. If we get past neonatal mortality data at Ola During Children's Hospital , we compare the survival rates using Kaplan-Meier method.

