**Nature and extent of the burden and risks associated with participation, benefit and group relatedness:** In this study, we are targeting premature babies that have previously been difficult to be saved at Ola During Children's Hospital which may reduce neonatal mortality. Patients are constantly monitored throughout the study to minimize risk. The use of the incubator may result in insufficient heat retention for the patient even though laboratory tests results showed effectiveness of its capability to keep the patient above 37 degree for 3 hours. In order to avoid this problem, a Japanese neonatologist will monitor the patient for 24 hours per day throughout the study period.

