#### **3.2 The importance of incubator**

Every hour, an estimated 340 babies die in the first week of birth, of preterm birth and asphyxia, which are the most frequently encountered causes for their deaths. Ninety-nine percent of these deaths occur in low- and middle-income countries(1). Compared with adults, newborns are particularly vulnerable to heat loss. Although passive, low-cost approaches such as the Embrace Infant Warmer are available to prevent heat loss of these newborn babes, they lack cooling functions and, therefore, it cannot control their , temperature(2). In many tropical countries, temperatures in the shade can reach >40 °C in the summer, and at this point, an incubator warmer can put babies at risk of hyperthermia. Advanced incubators exist, but they can cost thousands of dollars. The "Neonurture," a design that takes advantage of locally available replaceable parts of automobiles, is not a viable solution for mass production because it is still too complicate to be assembled and expensive (>\$1000) for "bottom of the pyramid" rural users(3). In addition to heat loss, nosocomial

infections are an important cause of infant morbidity and mortality in resource-poor countries, where neonatal deaths toll from sepsis reaches 29% of all neonatal deaths(4),(5). Preterm birth occurs in 11% of live births globally and accounts for 35% of all newborn deaths(6). Because preterm newborns have immature innate and adaptive immunity as compared with term babies, mortality due to inadequate immune system response is high in preterm newborns. Routine medical procedures including respiratory support carry an increased risk of infection and associated longterm morbidity in preterm infants(6). In addition, pediatric respiratory infections appear to contribute to some cases of sudden infant death syndrome(7). We are developing a thermodynamically advanced lowcost incubator suitable for operation in low-resource environments. The incubator features a modular design for multiple purposes. Primarily, it comprises of reusable control modules that have low maintenance requirements and low fixed costs. The incubator features four innovations:

- I. The new incubator is made of vinyl tubes and can be washed. it is reusable and easy to maintain. it can be used many times and is clean
- II. The incubator has a layer of air-contained tubes like a buoyancy ring and has been proven to have a high level of heat retention.

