##### 5.1.2 Exclusion criteria

- When informed consent cannot be obtained
- Newborns with fatal congenital diseases
- Newborns with critical conditions (breathing disorder, sepsis)
- Newborns under 800g over 2000g
- Fulfills one or more of the two inclusion categories defined in Table 2.

**Table 1.** Inclusion categories

Inclusion criteria	Case Definition
Birth weight	Newborns from 800g to 2000g

Table 2.

Exclusion criteria	Case definition
Weight	< 800 > 2000g
Baby's conditons	Breathing disorders, sepsis, and fatal congenital diseases

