### 1.2 Study period

The enrollment period will last a week. Demographic and baseline clinical data are recorded on admission while outcome data are captured at hospital discharge. The hospital discharge of the last patient enrolled will be considered the end of the data collection period for this study. The study period will end at completion of data analysis.

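### The survival comparison with past hospital mortality in section 7.2 has no stated matching, so a difference could not be attributed to the incubator, and about 6 infants carry almost no information on mortality

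*Protocol*

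**What the plan says.** Protocol section 7.2 has two sentences. The first is "This study only records biological parameters and temperature". The second is conditional: "If we get past neonatal mortality data at Ola During Children's Hospital", then "we compare the survival rates using Kaplan-Meier method". This is the protocol's only comparison between groups of infants. Section 6.1.4 rules out randomisation, and section 6.2 gives study groups as not applicable.

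Who is enrolled:
- Section 5.1 admits birth weights of 800 to 2000 g. Section 5.1.2 excludes "Newborns with critical conditions (breathing disorder, sepsis") and "Newborns with fatal congenital diseases".
- Section 6.1.2 requires stable breathing, an initial assessment and parental consent before the infant is placed in the incubator.

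How they are exposed and followed:
- Section 6.1.2 has the infant observed in the incubator for 24 hours and then returned to a cot.
- The study period section (numbered 1.2 in the text) says "outcome data are captured at hospital discharge".
- The project summary has a neonatologist monitoring the patient 24 hours a day. Section 2.1 describes a ward with one assigned medical doctor.

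The sample size section (numbered 1.1 in the text) expects at least 6 infants, a count taken from admission rates. The primary objective and hypothesis (4.1.1, 4.1.3) concern heat retention and temperature. Section 3.3 nevertheless says the results will show a possibility of successful treatment and, from that, a better chance of survival.

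**The concern.** A comparison with past data can be read as a device effect only if the two sets of infants are alike apart from the device. Here the study side is selected for stability and for having lived to consent, and it receives closer observation than the ward's stated staffing suggests is usual. Nothing stated puts the past side on the same footing. Exposure lasts 24 h but the outcome accrues until discharge, so much of the survival time lies outside the intervention.

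The number of infants is also very small. A curve for about 6 infants beside a historical one can look persuasive while saying almost nothing about mortality. The risk is a published survival statement, encouraged by section 3.3, that neither the design nor the data can support.

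**Working it through.** The protocol gives no past mortality rate, significance level or effect size, so there is no planned figure to reproduce. The inputs from the protocol are n = 6, the eligibility criteria, 24 h of exposure and outcome at discharge. Every mortality rate and case-mix share below is an assumption, as is the use of one-sided 5% as a benchmark.

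**1. Selection on severity, same weight range, device without effect.** Let s be the share of past infants who would have been excluded, m_x their mortality and m_e the mortality of eligible infants.

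Apparent mortality ratio = m_e / [(1 − s) m_e + s m_x]

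Assumed ranges: s = 0.3 to 0.7, m_x = 0.40 to 0.50, m_e = 0.10 to 0.20.
- Lowest: 0.10 / (0.3 × 0.10 + 0.7 × 0.50) = 0.10 / 0.38 = 0.26
- Highest: 0.20 / (0.7 × 0.20 + 0.3 × 0.40) = 0.20 / 0.26 = 0.77

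An inert device would appear to cut mortality by 23% to 74%.

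**2. Past data that also include heavier newborns.** Let s now be the critical share of all admissions, m_c their mortality, and w the share of non-critical admissions at 800 to 2000 g. Assume non-critical mortality of 0.20 in that weight range and 0.04 above it.

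Past mortality = s m_c + (1 − s)[0.20 w + 0.04 (1 − w)], compared with 0.20 in eligible infants.
- s = 0.2, m_c = 0.20, w = 0.2: 0.04 + 0.8 × 0.072 = 0.098, a difference of −10 points (the device looks harmful)
- s = 0.4, m_c = 0.50, w = 0.4: 0.20 + 0.6 × 0.104 = 0.262, a difference of +6 points (the device looks helpful)

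The sign depends on a feature of the past data that the protocol leaves open.

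**3. Chance that 6 infants look better than the past rate, inert device.** This is the binomial probability that deaths/6 falls below the past rate.

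| Past mortality | Eligible mortality half of it | Eligible mortality equal to it |
|---|---|---|
| 10% | 0.74 | 0.53 |
| 20% | 0.89 | 0.66 |
| 30% | 0.78 | 0.42 |
| 40% | 0.90 | 0.54 |
| 50% | 0.83 | 0.34 |

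Example at 30%: fewer than 30% of 6 means 0 or 1 death. With true mortality 0.15, 0.85^6 + 6 × 0.15 × 0.85^5 = 0.377 + 0.399 = 0.78.

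**4. Precision of the best possible result, 0 deaths in 6.**
- P(0/6) = (1 − p)^6, which is 0.262 at p = 20%, 0.118 at 30% and 0.047 at 40%.
- Exact two-sided 95% upper limit: 1 − 0.025^(1/6) = 45.9%.
- With the past rate treated as fixed, one-sided 5% needs (1 − p)^6 ≤ 0.05, so p ≥ 1 − 0.05^(1/6) = 39.3%. Below that past mortality, no outcome in 6 infants can reach it.
- Where it can be reached, selection alone may produce it. With past mortality 40% and eligible mortality 20%, 0/6 occurs with probability 0.8^6 = 0.26. With 50% and 25%, it is 0.75^6 = 0.18.

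**The case against.** The strongest defence is that the comparison is incidental. It depends on obtaining the data, survival is not an objective, hypothesis or listed parameter, and the primary temperature question is untouched. The protocol does not say that the past data will be unrestricted. It is silent, and a statistical analysis plan that is not shown could define the comparator. All of this limits the point's reach. It does not remove it, because the protocol itself commits to the comparison and names the source. Nothing it states makes the groups comparable, and a better-defined comparator would not change the 24 h exposure or the number of infants.

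Several stronger readings are tempting, and the protocol does not support them:
- **The analysis is bound to show a benefit even for an inert device.** Steps 2 and 3 show otherwise. The weight limit can offset or reverse the bias, and 6 infants can fall either way by chance.
- **The sepsis exclusion removes 29% of deaths.** Section 3.2 says "neonatal deaths toll from sepsis reaches 29% of all neonatal deaths", but as a figure for resource-poor countries, not for this hospital. Excluding septic infants also takes them out of the denominator, and infants free of sepsis at entry may develop it later.
- **Kaplan-Meier censoring at live discharge favours the device.** No censoring rule is stated. If both series were handled alike, no direction follows.
- **The exclusions remove the very infants the trial is meant for.** The summary says "we are targeting premature babies that have previously been difficult to be saved", but it singles out infants of around 1000 g, who remain eligible. Only the critically ill among them are excluded.

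**Conclusion.** The point holds as a matter of attribution and precision. As written, the comparison sets selected, closely monitored infants against past infants whose make-up and time origin are unspecified, so a difference in survival could not be ascribed to 24 h in the incubator. If the past infants are unselected but of the same weight, the bias probably favours the device. If they include heavier newborns, its direction cannot be known in advance. The ratio of 0.26 to 0.77 and the range of −10 to +6 points rest wholly on assumed rates and shares.

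The precision results need only n = 6 and, for the 39.3% threshold, a fixed past rate and a one-sided 5% benchmark. Recruiting more than 6 would narrow the interval but would leave the confounding as it is.

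**What to change.** In section 7.2, replace the Kaplan-Meier comparison with a count of in-hospital deaths among enrolled infants and its exact 95% confidence interval.

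If past data are shown, restrict them to infants who meet the section 5.1 criteria (same weight range and same exclusions), with the same time origin as enrolment and follow-up to discharge. Present the two death proportions descriptively, with no test and no survival claim.

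In section 3.3, reword the sentence on survival so that a better chance of survival is not presented as something the study results will demonstrate.

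The cost is wording in two sections, with no additional infants. If past data are shown, the records must allow the eligibility restriction. The sponsor gives up a survival statement that the data could not have supported.
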